6.3.7 Prolonged hospitalization

Any AE that results in prolonging of the study hospitalization shall be documented on the FDA Medwatch form as an SAE and be subject to all the rules and regulations of reporting as described in this section.

6.3.8 Pregnancy

Pregnancy inclusion criteria

Women of childbearing potential must have a negative serum pregnancy test within the 7 days prior to study drug administration.

Women of childbearing potential must either agree to abstain from sexual intercourse or use an effective birth control method during treatment and for an additional 30 days after the last dose of carfilzomib. Men who are sexually active with women of childbearing potential must either agree to abstain from sexual intercourse or use a condom with spermicide during treatment and for an additional 30 days after the last dose of carfilzomib, and the female partner should consider using an effective method of birth control.

Pregnancy exclusion criteria

Women who are pregnant and/or breast feeding

6.3.8.1 Pregnancy reporting

Subjects will be instructed to notify the investigator as soon as possible after learning becoming pregnant or the pregnancy of a partner during treatment of or up to 30 days following the last study drug administration.

Pregnancy Reporting by Investigator-sponsor to Amgen

Report Pregnancy and potential infant exposure including Lactation, within ten (10) calendar days of Sponsor awareness. Provide to Amgen the SAE reports associated with pregnancy. SUSARs are to be reported within twenty-four (24) hours of submitting the report to the applicable regulatory authority.

Amgen Drug Safety and Pharmacovigilance Contact Information:

- Drug Safety Reporting Fax
- Toll-free US [contact]
- Toll US [contact]

Drug Safety Reporting by secure e-mail can be established upon request

If the patient becomes pregnant while taking an Amgen drug, the drug will be immediately discontinued.

The investigator will discuss the risks and concerns of investigation drug exposure to a developing fetus and counsel the subject and/or pregnant partner (or ensure that such counseling is provided).

Pregnancies will be followed through the outcome of the pregnancy.

Newborns should be followed for a minimum of 12 weeks.

The Investigator will complete a Pregnancy Monitoring Form and report the information regarding the pregnancy, outcome, and status of the newborn as appropriate.

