5.3.2 Concomitant therapy

Conventional therapy for AMR: Therapeutic plasma exchange (PLEX) 1.5 plasma volumes replaced with 5% albumin or fresh frozen plasma for 8 sessions every-other day. Total intravenous immunoglobulins (IVIG) 100 mg/kg IV after each PLEX with the exception of the final PLEX where IVIG 500 mg/kg will be given. On day 16, if the IgG level is below 700 mg/dL, an additional dose of IVIG 500 mg/kg will be administered. If the IgG result is found to be 700ml/dL or higher, the IVIG 500mg/kg dose will not be administered. Premedications will be given for IVIG as follows: acetaminophen 650 mg PO and diphenhydramine 25 mg PO both 30 minutes prior to IVIG, unless otherwise directed on the part of one of the investigators if believed to be in the best interests of patient care. Conventional therapy requires an inpatient hospital stay. Patients will receive a tunneled PLEX catheter and peripherally inserted central catheter (PICC) inserted by interventional radiology in the routine clinical care of these patients prior to receiving any conventional or carfilzomib therapy.

Contraception

Female:

Women of childbearing potential must either agree to abstain from sexual intercourse or use an effective birth control method during treatment with carfilzomib. Given that carfilzomib was clastogenic in the in vitro chromosomal aberration test in peripheral blood lymphocytes, as a precaution, females of childbearing potential and/or their male partners should use effective contraception methods or abstain from sexual activity during and for 30 days after treatment with carfilzomib. If pregnancy occurs during this time, patients should be apprised of the potential hazard to the fetus. Kyprolis (carfilzomib) should only be used during pregnancy if the potential benefits to the mother outweigh the potential risks to the fetus.

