Based on its mechanism of action and findings in animals, carfilzomib can cause fetal harm when administered to a pregnant woman. Carfilzomib caused embryo-fetal toxicity in pregnant rabbits at doses that were lower than in subjects receiving the recommended dose. Carfilzomib administered to pregnant rats and rabbits during the period of organogenesis was not teratogenic at doses up to 2 mg/kg/day in rats or up to 0.8 mg/kg/day in rabbits. If carfilzomib is used during pregnancy, or if the subject becomes pregnant while taking this drug, she should inform the investigator or study staff immediately. The investigator should notify Amgen of the pregnancy and discuss follow-up with the subject. It is not known if carfilzomib will reduce the efficacy of oral contraceptives. Due to an increased risk of venous thrombosis associated with carfilzomib, subjects currently using oral contraceptives or a hormonal method of contraception associated with a risk of thrombosis should consider an alternative method of effective contraception.

Male:

Males of reproductive potential should be advised to avoid fathering a child while being treated with carfilzomib. The potential for carfilzomib to be transferred via semen and its effect on sperm are unknown. Male subjects treated with carfilzomib and/or their female partners (if of childbearing potential) should use effective contraceptive methods or abstain from sexual activity while treated with carfilzomib and refrain from donating sperm while on carfilzomib and for 90 days after treatment. If pregnancy occurs during this time, patients should be apprised of the potential hazard to the fetus, study drug should be interrupted, and a serum pregnancy test

performed. Study drug administration may resume if result is negative and study drug be discontinued, if positive.

Male subjects should be advised to inform the investigator or study staff immediately in the event that their female partner becomes pregnant during the study. Upon receipt of this information, the investigator should notify Amgen of the pregnancy and discuss follow-up regarding the pregnancy outcome with the subject.

Breastfeeding:

If a woman breastfeeds during the study, she must inform the investigator or study staff immediately. The investigator should notify Amgen that the subject has breastfed the infant and discuss follow-up with the subject.

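### The pregnancy stop rule in section 6.3.8.1 does not literally cover a woman already pregnant when dosed, section 5.3.2 conditionally permits use in pregnancy, and the only hold-and-test step sits under Male without saying who is tested

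*Combined protocol and SAP*

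**What the plan says.** Two sections of the combined protocol and SAP deal with pregnancy on treatment.

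- **Section 6.3.8.1, Pregnancy reporting:** "If the patient becomes pregnant while taking an Amgen drug, the drug will be immediately discontinued". No exception is given. For a pregnancy in a male patient's partner, the section asks for notification, reporting and follow-up, and has the investigator "counsel the subject and/or pregnant partner". It does not mention the man's dosing.
- **Section 5.3.2, Concomitant therapy, Contraception, Female:** "If pregnancy occurs during this time, patients should be apprised of the potential hazard to the fetus". The next sentence is "Kyprolis (carfilzomib) should only be used during pregnancy if the potential benefits to the mother outweigh the potential risks to the fetus". The text then sets out what happens "If carfilzomib is used during pregnancy, or if the subject becomes pregnant while taking this drug": the subject tells the study staff, and the investigator notifies the manufacturer and discusses follow-up. No hold, test or stop is given under this heading.
- **Section 5.3.2, Male:** the opening words on pregnancy are the same as under Female, but here they continue: "study drug should be interrupted, and a serum pregnancy test" is to be performed. Then: "Study drug administration may resume if result is negative and study drug be discontinued, if positive". The person to be tested is not named.

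Pregnant women are excluded at entry. A negative serum test is required within 7 days before study drug for women of childbearing potential (sections 5.1.3.2, 5.4.1 and 6.3.8). The enrollment criteria must be met again before a second cycle (section 5.3.1.1).

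**The concern.** Section 5.3.2 is in the treatment part of the protocol, where staff look when deciding on the next dose. Section 6.3.8.1 is a reporting section. Someone working from 5.3.2 alone would find a benefit-risk judgment for a pregnant patient and no instruction to stop. Someone working from 6.3.8.1 would find a stop, but one worded for a pregnancy that starts during treatment. Neither section tells staff to hold the next dose of a woman whose pregnancy is suspected but unconfirmed.

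Under Male, a test that allows dosing to resume has to be done on someone, and the text does not say on whom. Staff could act differently on it.

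What is at stake is fetal exposure in a rare case, since section 5.3.2 itself says the drug can harm a fetus, and possibly a man's rejection treatment. No endpoint, estimate or sample-size statement is involved.

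**Working it through.** The plan gives no figure to reproduce here. The check sets the texts side by side, followed by short arithmetic on how much dosing depends on them.

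**What each section tells staff to do**

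| Situation | Section 5.3.2 | Section 6.3.8.1 |
|---|---|---|
| Woman conceives while on drug | Inform her of the hazard; use only if benefit outweighs risk; notify | Stop at once |
| Woman already pregnant at first dose, found later | Same benefit-risk condition; notify | Not literally covered, because the pregnancy did not begin on drug |
| Pregnancy suspected in a woman, not confirmed | No hold and no test under Female | No hold and no test |
| Male patient, partner pregnant | Interrupt, serum test, resume or discontinue; person tested not named | Notification, reporting, counselling, follow-up; silent on his dosing |

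Row 1: stopping complies with both sections. Continuing complies only with 5.3.2, and no text says which section prevails.

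Row 2: this is probably the less rare of the two cases in women. Treatment is given during an inpatient stay of at least 16 days (section 5.4) and under contraception or abstinence rules (section 6.3.8), so conception during a cycle is unlikely. What remains is mainly an early pregnancy that the screening test missed. The stop rule does not literally reach that case, and the benefit-risk sentence does.

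Rows 3 and 4: a test that lets dosing resume if negative is a natural step for suspected pregnancy in a woman receiving the drug. It appears only under the other heading.

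**How old the screening test can be**

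Section 5.4.1 does not say which dose the test must precede. Assume it precedes the first dose of the cycle:

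- age at the last dose = 7 + (16 − 1) = 22 days.

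If a test is meant before every dose, the maximum is 7 days. The range is therefore 7 to 22 days.

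**How many doses depend on the wording in cycle 1**

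The schedule is 20 mg/m² on days 1, 2, 8, 9, 15 and 16 (section 5.3.1.1), so 6 × 20 = 120 mg/m². Doses left after dose *n* = 6 − *n*.

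- Pregnancy found after dose 1: 6 − 1 = 5 doses, 5 × 20 = 100 mg/m².
- Pregnancy found after dose 5: 6 − 5 = 1 dose, 20 mg/m².

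A woman found pregnant before cycle 2 is excluded by the repeated enrollment criteria. A man whose partner is found to be pregnant before cycle 2 could lose all 6 doses of that cycle if the Male text means that his drug stops.

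The documents do not say how many of the 30 patients are women of childbearing potential, or men with such partners, so no event rate can be given.

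**The case against.** The strongest reply is that there is no conflict. The sentence in 5.3.2 restricts use and does not instruct anyone to continue; it reads like general product advice. Section 6.3.8.1 is specific and mandatory. The breastfeeding text in 5.3.2 likewise mixes product advice with trial rules. Section 5.9 also lets investigators withdraw any patient for safety.

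Much of that stands. A reader might infer that the two sections contradict each other; they do not, because stopping satisfies both. But the comparison with breastfeeding cuts the other way: there, the weighing of benefit is followed by a plain statement that the drug should not be used. Section 5.3.2 has no such statement for pregnancy, and 6.3.8.1 does not literally fill the gap for a woman already pregnant when dosed. Section 5.9 permits a stop but does not require one.

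A reader might also infer that the Male rule was placed under the wrong heading and should be deleted. The documents do not establish that. The same paragraph says it is unknown whether the drug passes into semen, so holding a man's drug while a partner's pregnancy is checked may be a deliberate precaution. Since only enrolled subjects receive study drug, the ordinary reading is his drug and her test. What survives is narrower: the person tested is unnamed, and the intended effect on his dosing should be confirmed.

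Finally, a reader might see a clash over partner-pregnancy notification. Section 6.3.8.1 covers treatment and the 30 days after it, while 5.3.2 asks men to "inform the investigator or study staff immediately in the event that their female partner becomes pregnant during the study". These requirements add to each other, so that is a matter of wording only.

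**Conclusion.** The concern holds as a minor patient-safety point. Section 5.3.2 conditionally permits use in pregnancy where 6.3.8.1 requires a stop; the stop rule's trigger does not literally include a woman already pregnant when dosed; and women have no hold-and-test step under their own heading. The Male step leaves the person tested unstated.

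Few patients are likely to be affected, given the screening test, the contraception rules, the inpatient stay and the repeat of the enrollment criteria before cycle 2. For a woman in cycle 1, between 1 and 5 of the 6 doses could depend on which text is followed, if the pregnancy is found between the first and last dose. The 22-day upper limit on test age rests on the assumption that the test precedes only the first dose of the cycle. The view that a missed early pregnancy is the main remaining case in women is a judgment from the safeguards, not a figure in the documents. There is no effect on the analysis.

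**What to change.** Three wording changes:

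1. **Section 5.3.2, Female, and section 6.3.8.1.** Replace the benefit-risk sentence in 5.3.2 with an immediate and permanent stop. Use one trigger in both sections: *the patient is found to be pregnant or becomes pregnant while receiving carfilzomib*. The existing sentence on telling study staff can stay, since it already covers a woman dosed while pregnant.
2. **Section 5.3.2, Female.** Add a step for suspected pregnancy: interrupt carfilzomib, do a serum pregnancy test, resume if negative, stop permanently if positive.
3. **Section 5.3.2, Male.** Keep the rule for now. State that the test is the female partner's, and have the sponsor confirm whether the man's own dosing is meant to stop, given the unknown transfer in semen. Deleting the rule outright could remove a fetal safeguard.

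The cost is small. Investigators lose the discretion to continue in a pregnant patient, which 6.3.8.1 already denies for a pregnancy that begins on treatment. A dose may be briefly delayed while a test is run. No scheduled visit is added, and a serum test is added only when pregnancy is suspected.

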6.4.1 Reporting requirements for serious adverse events

The Investigator-sponsor must be notified of the occurrence of any SAE within 24 hours of the investigator, designee, or site personnel's knowledge of the event.

SAE Reporting by Investigator-sponsor to Amgen

The Investigator-sponsor must inform Amgen in writing by e-mail or fax at the contact information listed below for all SUSARs that are judged as reasonably related to the Amgen study drug. Site will transmit the final CIOMS of that event to Amgen within twenty-four (24) hours of submitting the report to the applicable regulatory authority.

6.5 Follow-up of patients after adverse events

All SAEs regardless of relationship to CFZ must be followed to resolution or to stabilization if improvement or resolution is not expected.

7 Investigator requirements

7.1 Study initiation

Before the start of the study and any study-related procedures the following documents must be signed by the co-principal investigators. A copy must be retained both by Amgen and the study site team.

US FDA Form 1572: Statement of investigator signed by the co-primary investigators. The names of the co-investigators must appear on this form.

Current curriculum vitae and evidence of licensure for all investigators.

Complete financial disclosure forms as required by FDA Form 1572 for all investigators.

Written University of Pittsburgh IRB statement of approval and compliance of the protocol and informed consent form.

Investigator brochure receipt signed and dated by the co-principal investigators.

Protocol acceptance form signed and dated by the co-principal investigators.

7.2 Study completion

The following data and materials will be submitted to Amgen upon the conclusion of the study.

Laboratory findings, clinical data, and all special test results from screening through the end of the study period for all study subjects.

Completed drug accountability forms.

Copies of any protocol amendments and IRB approval notifications.

Signed and dated protocol amendment acceptance forms.

Summary of the study prepared by the co-principal investigators (IRB summary close letter).

Updated financial disclosure forms for all investigators.

7.3 Informed consent form

The informed consent forms for the study must be approved by the University of Pittsburgh IRB.

Consent forms must be signed by the patient or legal designee before his/her participation in the study. A signed copy of the informed consent form will be inserted into the medical record and retained with the study investigators files. A copy of the informed consent form will be given to the patient or legal designee.

Consent forms must be available for review by the sponsor at any time.

Consent forms should be revised whenever there are changes to the procedures outlined in the informed consent form or when new information is available that may affect the willingness of patients to participate.

7.4 Communication with the IRB

This protocol, the informed consent forms, and any information to be given to the patient must be submitted to the IRB by the co-principal investigators for review and approval before the study is initiated. In addition, any patient recruitment materials must be approved by the IRB.

The principal investigator is responsible for providing written summaries of the status of the study to the IRB at least annually in accordance with all IRB policies and procedures. Investigators are also responsible for promptly informing the IRB of any protocol changes or amendments and any unanticipated problems involving risk to patients or others.

Any other IRB requirements not delineated in this section must be fulfilled by the co-primary investigators.

7.5 Study monitoring requirements

Site visits may be conducted by an authorized Amgen representative to inspect the study data, patient records, and AE reports. The co-primary investigators permit Amgen, IRB, FDA, or other respective relevant health authorities to inspect study facilities and records relevant to this study.

7.6 Source data documentation

Study monitors may perform ongoing source data verification to confirm that critical protocol data are entered accurately and completely in the study database.

Source documents are defined as the location in the official medical record or other credible source of information where patient data are recorded and documented for the first time.

Source documents will never be destroyed or altered.

7.7 Study medication accountability

All study drug required for completion of this study will be provided by Amgen. The UPMC investigational drug service (IDS) pharmacy will acknowledge receipt of the drug by returning the relevant documentation forms indicating shipment content and condition. Damaged supplies will be replaced.

Accurate records of all study drug received at, dispensed from, returned to and disposed of by the UPMC IDS pharmacy shall be recorded.

7.8 Disclosure of data

Patient medical information obtained by this study is confidential and may only be disclosed to third parties as permitted in the informed consent form signed by the patient or legal designee as required by law.

Medical information may be given to a patient's personal physician or other appropriate healthcare provider for purposes of patient treatment and welfare.

Data generated by this study must be available for inspection upon request by representatives of the FDA or other relevant regulatory agencies and the study sponsor.

9.1 Appendix A: Study Flowcharts

Study Procedures								In		enti ±14 d	on Pl lays	hase							Festin Phase	e		Po	st-stu	dy Fo
	0	1	2	3	4	5	6	7	8	9	10	11	12	13	14	15	16	28	42	90	120	150	180	210
Screening/Enrollment	х																							
Standard of Care Procedure	es.																							
H&P		Х																						
Progress note			Х	Х	Х	Х	Х	Х	Х	Х	х	Х	Х	Х	Х	х	х	Х	Х	Х	Х	Х	Х	Х
PLEX 1.5 volumes		Х		Х		Х		Х		Х		Х		Х		Х								
Premeds for IVIG		Х		Х		Х		Х		Х		Х		Х		Х	Х							
IVIG 100 mg/kg		Х		Х		Х		Х		Х		Х		х										
IVIG 500 mg/kg																Х	Χ*							
Medrol 750-1000 mg IV		Х	Х	Х	on	ly gi	ven	if co	ncor	nita	nt AC	îR												
CBC w/differential		Х	Х	Х	Х	Х	Х	Х	Х	Х	х	Х	х	х	Х	Х	Х	Х	Х	Х	Х	Х	Х	
CMP		Х	Х	Х	Х	Х	Х	Х	Х	Х	х	Х	Х	Х	Х	Х	Х	Х	Х	Х	Х	Х	Х	
Total IgG		Х															Х	Х	Х	Х	Х	Х	Х	
Complement 3 & 4		Х															Х	Х	Х	Х			Х	
Luminex IgG-SAB		Х															Х	х	Х	Х	Х	Х	Х	Х
Luminex C1q-SAB		Х															х	Х	Х	Х	Х	Х	Х	Х
PFTs		Х																Х	Х	Х	Х	Х	Х	Х
TB Biopsy		Х																	Х					clin
Study Specific Procedures																								
Premeds for CFZ		Х	Х						Х	Х						Х	Х							
CFZ 20 mg/m2		Х	Х						Х	Х						Х	Х							
CFZ AE assess			Х	Х	Х	Х	Х	Х	Х	Х	х	Х	Х	Х	Х	Х	Х	Х	Х	Х				
CFZ response assess																		х	х	х				
IgG-SAB subclasses**		Х															х	х	х	х				
Blood for PBMC**		Х															х	Х	Х	Х				

Progress notes indicate inpatient admission or clinic visits within ±14 days of the stated days, unless the patient is unable to present due to unforeseen circumstances (e.g., death, hospitalization at another facility, etc.). Standard of care procedures will not be done solely for research purposes.

Study ends at the day 90 visit. Post-study follow-up will continue for all patients alive at day 90 to 1 year post enrollment through a medical records review.

Study CFZ AE assessment will be conducted either in-person or via telephone (day 1 through 16, and 28, 42 and 90

^{*} Dose will be administered only If IgG level is below 700 mg/dL.

^{**} Research samples will only be obtained if subject is coming to their standard of care visit on days 28, 42 and 90.

Appendix B: Study data collection summary

Baseline characteristics

- 1. Lung transplant indication: interstitial lung disease, chronic obstructive pulmonary disease, cystic fibrosis, scleroderma, sarcoidosis, pulmonary arterial hypertension, other (specify)
- 2. Transplant type: single, bilateral
- 3. Date of transplant
- 4. Time after transplant to enrollment
- 5. Age at transplant
- 6. Age at enrollment
- 7. Gender: male, female
- 8. Race: Caucasian, African American, Native American, Hispanic, other (specify)
- 9. Induction immunosuppression
- 10. Maintenance immunosuppression at enrollment
- 11. De novo DSA vs. preformed DSA prior to transplant
- 12. PFTs at enrollment (if not intubated): FEV1, FVC, FEF25/75
- 13. Bronchiolitis obliterans syndrome grade at enrollment
- 14. Daily oxygen use (Y/N)
- 15. CMV donor/recipient status: mismatch, recipient positive, negative
- 16. EBV donor/recipient status: mismatch, recipient positive, negative
- 17. HSV donor/recipient status: mismatch, recipient positive, negative
- 18. VZV donor/recipient status: mismatch, recipient positive, negative
- 19. Chronic infections at enrollment (specify)

Study characteristics

	1	2	3	4	5	6	7	8	9	10	11	12	13	14	15	16	28	42	90
WBC	Х	Х	Х	Х	Х	Χ	Χ	Х	Χ	Х	Х	Х	Х	Х	Х	Х	Х	Х	Х
ANC	Х	Х	Х	Х	Х	Χ	Χ	Х	Χ	Х	Х	Х	Х	Х	Х	Х	Х	Х	Х
ALC	Х	Χ	Х	Χ	Χ	Х	Х	Χ	X	Х	Х	Х	Х	Х	Х	Х	Х	Х	Х
Hematocrit	Х	Χ	Х	Χ	Χ	Х	Х	Χ	X	Х	Х	Х	Х	Х	Х	Х	Х	Х	Х
Platelets	Х	Χ	Х	Х	Χ	Χ	Χ	Х	Χ	Х	Х	Х	Х	Х	Х	Х	Χ	Х	Х
BUN	Х	Χ	Х	Х	Χ	Χ	Χ	Х	Χ	Х	Х	Х	Х	Х	Х	Х	Χ	Х	Х
Creatinine	Х	Χ	Х	Χ	Χ	Х	Х	Χ	X	Х	Х	Х	Х	Х	Х	Х	Х	Х	Х
Total IgG	Х															Х	Х	Х	Х
IgG 1	Х															Х	Х	Х	Х
IgG 2	Х															Х	Х	Х	Х
IgG 3	Х															Х	Х	Х	Х
IgG 4	Х															Х	Х	Х	Х
Complement 3	Х															Х	Х	Х	Х
Complement 4	Х															Х	Х	Х	Х
DSA MFI neat	Х															Х	Х	Х	Х
DSA MFI 1:16	Х															Х	Х	Х	Х
DSA MFI EDTA	Х															Х	Х	Х	Х
DSA MFI C1q neat	х															х	х	х	х
DSA MFI AHG- C1q neat	х															х	Х	х	х
DSA MFI C1q 1:16	х															х	Х	х	х
DSA MFI C1q EDTA	х															х	х	х	х

DSA IgG	х									-						х	х	х	х
subtype	X															X	X	X	X
FEV1	Х																Х	Х	Х
FVC	Х																Х	Х	Х
FEF 25/75	Х																Х	Х	Х
ACR A grade	Х																	Х	
ACR B grade	Х																	Х	
ACR C grade	Х																	Х	
AMR findings	.,																		
(Y/N)	Х																	Х	
Blood for	· ·																· ·	· ·	· ·
PBMC (Y/N)	Х															Х	Х	Х	Х
PLEX (Y/N)	Х		Х		Х		Х		Χ		Х		Х		Х				
IVIG 100 mg/kg			.,						Х		,								
(Y/N)	Х		Х		Х		Х		^		Х		Х						
IVIG 500 mg/kg															X**				
(Y/N)															^				
Carfilzomib 20	х	Х						х	Х						х	Х			
mg/m ² (Y/N)	^	^						^	^						^	^			
Other																			
carfilzomib	х	х						х	Х						x	х			
dose and	^	^						^	^						^	^			
reason																			
Medrol (Y/N)	Х	Х	Х																
Medrol dose	Х	Х	Х																
AE assessment	Х	Х	Х	Х	Χ	Χ	Х	Х	Χ	Χ	Х	Х	Х	Х	Х	Х	Х	Х	Х
Death	Х	Х	Х	Х	Χ	Χ	Х	Х	Χ	Χ	Х	Х	Х	Х	Х	Х	Х	Х	Х
AE/SAE	Х	Х	Х	Х	Х	Х	Х	Х	Х	Х	Х	Х	Х	Х	Х	Х	Х	Х	Х
Cultures*	Х	Χ	Х	Х	Χ	Χ	Χ	Χ	Χ	Х	Х	Х	Х	Х	Х	Х	Х	Х	Х
*Culturas, bastaris			_		==										- d - t				

^{*}Cultures: bacterial, viral, fungal, AFB, cytology. Positive cultures will be recorded at any time if they are taken.

^{**} Dose will be administered only If IgG level is below 700 mg/dL.
